2.2.1 Primary Safety and Effectiveness Endpoints

Primary Effectiveness Endpoint

The primary effectiveness endpoint is a binary clinician response after each UDS study using the T-DOC® NXT Catheter to determine whether the ability to measure UDS pressure was clinically adequate (success) or inadequate (failure). The primary effectiveness hypothesis is a comparison of the lower bound for the estimate of the success rate to a minimally acceptable target value of 75%.

H_0 : Effectiveness Success Rate is $\leq 75\%$

versus

H_A : Effectiveness Success Rate is $> 75\%$

This hypothesis will be evaluated by comparing the lower limit of the 1-sided 95% Clopper-Pearson confidence interval to 75%. The null hypothesis will be rejected if the lower limit of the 1-sided 95% Clopper-Pearson confidence interval is $> 75\%$, which indicates that a rate $\leq 75\%$ would be inconsistent with the trial findings.

Primary Safety Endpoint

The primary safety endpoint is a binary clinician response after each UDS study using the T-DOC® NXT Catheter to determine whether the safety of the device was clinically adequate (success) or inadequate (failure). The primary safety hypothesis is a comparison of the lower bound for the estimate of the success rate to a minimally acceptable target value of 75%:

H_0 : Safety Success Rate is $\leq 75\%$

versus

H_A : Safety Success Rate is $> 75\%$

This hypothesis will be evaluated by comparing the lower limit of the 1-sided 95% Clopper-Pearson confidence interval to 75%. The null hypothesis will be rejected if the lower limit of the 1-sided 95% Clopper-Pearson confidence interval is $> 75\%$, which indicates that a rate $\leq 75\%$ would be inconsistent with the trial findings.

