12.1.2 Primary Safety Endpoint

The primary safety endpoint is a binary clinician response after each UDS study using the T-DOC® NXT Catheter to determine whether the safety of the device was clinically adequate (success) or inadequate (failure). The primary safety hypothesis is a comparison of the lower bound for the estimate of the success rate to a minimally acceptable target value of 75%:

H_0 : Safety Success Rate is $\leq 75\%$

versus

H_A : Safety Success Rate is $> 75\%$

This hypothesis will be evaluated by comparing the lower limit of the 1-sided 97.5% Clopper-Pearson confidence interval to 75%. The null hypothesis will be rejected if the lower limit of the 1-sided 97.5% Clopper-Pearson confidence interval is $> 75\%$, which indicates that a rate $\leq 75\%$ would be inconsistent with the trial findings.

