12.3 Sample Size Determination & Power

The null hypotheses for the primary safety and the primary effectiveness endpoints are designed to rule out success rates $\leq 75\%$. There will be no type I error adjustment for simultaneous testing of these endpoints within the same trial. Based on clinical judgement and previous testing, the true success rate for both safety and efficacy is assumed to exceed 95%. Thus, the power calculation is identical for the safety and effectiveness endpoints, and a true success rate of 96% is assumed for each endpoint.

Analysis of 20 subjects would provide 81% power to rule out a success rate $\leq 75\%$ when the true success rate is assumed to be 96%, based on a 1-sided test with type I error rate of 5%. This study requires a minimum of 20 subjects to ensure adequate power, but the final sample size will be based on site enrolment capabilities. If 30 subjects or 40 subjects are enrolled, the power to rule out a success rate $\leq 75\%$ will be 96% and 99%, respectively (Fleiss, J.L. *et al.*, 2003).

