To evaluate the usability of the device by collecting clinical user feedback and evaluating the following subjective measures using defined ordinal scales: ease of use, ease of insertion, presence of artefacts, stability of the tracing, perceived time savings, ease of voiding around catheter, presence of use errors and overall satisfaction.	The usability performance endpoint will be captured in a questionnaire format. The trained clinical users will rate the T-DOC® NXT performance on a scale of 1-5 on the study outcome questionnaire.
Exploratory Objective 2	
To explore whether the newly designed, smaller sized T-DOC® NXT catheters causes undue discomfort based on subjective subject feedback regarding the discomfort and pain level, for those able to communicate such feedback.	This exploratory endpoint will be measured by collecting patient feedback regarding the level of discomfort and pain experienced during their Urodynamic test using the Numeric Pain Rating Scale (NPRS). Patients capable of providing feedback on a scale, will grade their discomfort/pain at 5 or lower, on the NPRS from 0 ("No Hurt") to 10 ("Hurts worst").

Analysis Populations

All subjects enrolled and completed the urodynamic procedure will be considered in the final analysis. Enrolled subjects who do not undergo the urodynamic procedure or begin the urodynamic procedure but do not complete it (for any reason determined by the investigator to be unrelated to the T-DOC® NXT catheters) will not be included in the final analysis and can be replaced.

If any CRFs are found to be incomplete, the study monitor will follow-up as to the reasoning. If for some reason a clinical user is unable to complete their questionnaire, the questions they have completed will be included in the analysis.

Primary Endpoint

The primary safety and effectiveness endpoint is a binary clinician response after each UDS study using the T-DOC® NXT catheter to determine whether the ability to measure UDS pressure was clinically adequate (success) or inadequate (failure).

In the statistical analysis plan, the null hypotheses for the safety and effectiveness endpoints are designed to rule out success rates $\leq 75\%$.

The allowable Type I error (α) for each hypothesis will be 5% (1-sided), and the Type II error is calculated to be 10% (90% power).

Safety and effectiveness will be evaluated separately via the following sets of hypotheses:

Primary Hypothesis for Safety

H_0 : Safety Success Rate is $\leq 75\%$

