versus

H_A : Safety Success Rate is $> 75\%$

Primary Hypothesis for Effectiveness

H_0 : Effectiveness Success Rate is $\leq 75\%$

versus

H_A : Effectiveness Success Rate is $> 75\%$

The study will be declared a success if both null hypotheses for safety and efficacy are ruled out.

Exploratory Endpoints

Exploratory Objective 1 for Usability Performance

This exploratory endpoint was collected to reflect that the goal of qualitatively describing users' interactions with the device as described in regulatory guidance for usability testing (*FDA's guidance- 'Applying Human Factors and Usability Engineering to Medical Device's, 2016*). A clinical user who completed the T-DOC® NXT clinical study, shall rate the T-DOC® NXT catheter usability performance on a scale of 1-5 for the clinical user questionnaire, comparing their experience with use of their currently used urodynamics catheter on per urodynamic day basis.

Since there will be only daily responses from one user for each of the questions, the results are thus not well-suited to statistical analysis and hypothesis testing is not appropriate. Instead, descriptive statistics will be used to summarize and analyse the results of each question, including: ease of use, ease of insertion, presence of artefacts, presence of coughs/Valsalva response, measurements and tracings of urethral pressure profiles, stability of the tracing, perceived time savings, ease of voiding around catheter, presence of errors and overall satisfaction.

The reported value in the usability performance survey will be analysed using proportions of levels and cumulative proportions of groupings at 95% confidence interval. This includes levels (1 to 5), "Yes and no", "better, same or worse" and any other questions related to usability.

Additionally, the results will be plotted over time to observe the trend as the study continues (preferably a line plot with daily responses over time).

Exploratory Objective 2 for Discomfort/Pain

To satisfy this exploratory endpoint for subject experience, a categorical response variable using the Numeric Pain Rating Scale (NPRS) from 0 ("No Hurt") to 10 ("Hurts worst") will be used. Subjects will grade their discomfort/pain on the scale from 0 ("No Hurt") to 10 ("Hurts worst"). Descriptive statistics will be used to summarize and analyse the results of questionnaires completed per patient for questions about pain during insertion, during test and during removal of the T-DOC® NXT catheters.

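### The SAP's 90% power has no sample size or assumed rate, does not hold at the permitted minimum of 20 subjects, and is not the power of the both-must-pass success rule

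*SAP*

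**What the plan says.** **SAP, Primary Endpoint.** Both nulls are success rates of 75% or less. Type I error is stated as "for each hypothesis will be 5% (1-sided"), followed by the statement that "the Type II error is calculated to be 10% (90% power"). No sample size, assumed true rate or test accompanies the 90%. The section ends with the success rule: "The study will be declared a success if both null hypotheses for safety and efficacy are ruled out".

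**Protocol 12.3.** With the same nulls, one-sided 5% alpha and a true rate of 96% for each endpoint: "Analysis of 20 subjects would provide 81% power to rule out a success rate" of 75% or less. With 30 or 40 subjects the power "will be 96% and 99%, respectively". Twenty is the minimum, and "the final sample size will be based on site enrolment capabilities". Sections 2.1 and 7.4 set the maximum at 40.

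**Protocol, safety limit.** Section 2.2.1 tests safety by "comparing the lower limit of the 1-sided 95% Clopper-Pearson confidence interval to 75" per cent. Section 12.1.2 tests the same hypothesis by "comparing the lower limit of the 1-sided 97.5% Clopper-Pearson confidence interval to 75" per cent.

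**The concern.** A power figure has meaning only with a sample size, an assumed true rate and a test. The SAP's figure has none of these, and it equals none of the three values in the protocol on which the SAP says it is based. Borrowing the protocol's 96% still leaves the sample size unknown.

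The 90% also sits beside a rule that both nulls must be rejected. Power for such a rule cannot exceed that of the weaker endpoint, and is lower unless the two ratings pass and fail together. A reader of the SAP would put the risk of missing a truly adequate device at 10%. If the study stopped at its permitted minimum and failed, that failure would be judged against the wrong figure.

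**Working it through.** **Inputs.** Null rate 75% (both documents). One-sided alpha 5% (SAP, Primary Endpoint; protocol 12.3). True rate 96% per endpoint (protocol 12.3 only). N from 20 to 40 (protocol 2.1, 7.4). Test: one-sided Clopper-Pearson lower limit above 75% (protocol 2.2.1, 12.1). Success rule: both nulls rejected (SAP).

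**Step 1: reproduce the protocol.** For each N, find the smallest number of successes r whose lower limit exceeds 75%. Power is P(X ≥ r) for X ~ Binomial(N, 0.96).

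At N = 20, r = 19 (lower limit 78.4%, exact alpha 2.43%). Power = 20 × 0.96^19 × 0.04 + 0.96^20 = 0.3683 + 0.4420 = 0.8103.

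| N | Needed | Exact power | Protocol |
|---|---|---|---|
| 20 | 19/20 | 81.03% | 81% |
| 30 | 27/30 | 96.94% | 96% |
| 40 | 35/40 | 99.51% | 99% |

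The protocol's figures are these values with the decimals dropped.

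**Step 2: look for the SAP's 90%.** Under the same test and true rate:

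| N | Needed | Exact power |
|---|---|---|
| 21 | 20/21 | 79.6% |
| 22 | 21/22 | 78.1% |
| 23 | 21/23 | 93.8% |
| 28 | 26/28 | 90.0% |
| 29 | 26/29 | 97.3% |

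From N = 23 to 40 the lowest value is 90.01%, at N = 28. The claim of at least 90% per endpoint therefore holds at 23 to 40 and fails at 20, 21 and 22. At N = 20 it would need a true rate of about 97.3%. Approximate methods at N = 20 give 87.7% (normal), 72.2% (normal with continuity correction) and 89.2% (arcsine). Only the arcsine comes near 90%, and it is not the specified test.

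**Step 3: power for both nulls.** Give each patient paired ratings with failure probability 0.04 each, and let q be the probability that both fail. Then exactly one given rating fails with probability 0.04 − q, and neither fails with probability a = 0.92 + q. At N = 20 each endpoint allows at most one failure, so

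P(both pass) = a^20 + 20 a^19 (0.08 − q) + 380 a^18 (0.04 − q)².

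- q = 0 (failures never coincide): 0.1887 + 0.3282 + 0.1355 = 0.6524.
- q = 0.04² = 0.0016 (independent): 0.6566.
- q = 0.0016 + 0.5 × 0.04 × 0.96 = 0.0208 (correlation 0.5): 0.7132.
- q = 0.04 (failures always coincide): 0.8103.

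The miss risk at N = 20 is therefore 1 − 0.8103 = 19% to 1 − 0.6524 = 35%, and 34% if independent. The same paired model, with 95% limits for both endpoints, gives:

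| N | Lowest | Independent | Highest |
|---|---|---|---|
| 20 | 65.2% | 65.7% | 81.0% |
| 28 | 80.8% | 81.0% | 90.0% |
| 29 | 94.6% | 94.6% | 97.3% |
| 30 | 94.0% | 94.0% | 96.9% |
| 40 | 99.0% | 99.0% | 99.5% |

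Under independence, joint power is below 90% at every N from 20 to 28 and at least 91.8% from 29 to 40.

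**Step 4: if safety uses the 97.5% limit of protocol 12.1.2.** N = 20 is unchanged (19/20 under either limit). At N = 30 safety needs 28/30. Its power is 88.3%, and joint power is 85.6% if independent (range 85.5% to 88.3%). At N = 40 safety needs 36/40. Its power is 97.9%, and joint power is 97.4% if independent (range 97.4% to 97.9%). Safety power alone is then also below 90% at N = 23 to 26 (76.6% at 23, 72.1% at 26) and at 29 to 32.

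**The case against.** The strongest reply is that 90% lies within the protocol's own range of 81% to 99% and is met per endpoint at 18 of the 21 permitted sample sizes. The SAP does not say it applies at 20. Protocol 12.3 also expects the true rate to exceed 95%, and at about 97.3% even 20 subjects would give 90%. All of this is correct. It makes the figure untraceable rather than impossible, but it remains a single unqualified number that fails at the minimum the protocol calls adequate, under the protocol's own 96%.

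On joint power, both ratings come from one clinician after the same procedure, so independence is a doubtful reference case and strong dependence would move the figure towards 81%. That is fair, and is why the full range is shown. Even the best case at 20 subjects is 81%. It is also true that protocol 12.3 already implies its figures are per endpoint, and that the both-must-pass rule does not inflate type I error.

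On the safety limit, the SAP's 5% for each hypothesis and protocol 12.3 both point to 95%. They do not remove the 97.5% from section 12.1.2.

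Finally, the SAP is dated 8 November 2018 and recruitment was planned for July to September 2018. If that timetable held, restating power would change no sample size, analysis or decision rule. This limits the consequence to how the design is described and how a failure would be interpreted.

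**Conclusion.** The concern holds. The SAP's 90% cannot be traced to a sample size or true rate and differs from every power figure in the protocol. Under the protocol's test and 96% true rate it is wrong at 20, 21 and 22 subjects. At the permitted minimum of 20, type II error is 19% per endpoint and 19% to 35% for the SAP's success rule, against the stated 10%. Power for that rule appears in neither document.

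These figures assume a 96% true rate for each endpoint, independent patients, the exact Clopper-Pearson rule and every analysed subject rated on both endpoints. The joint figures also depend on the within-patient association, which the documents do not give, and above 20 subjects they can depend on which safety limit applies. Type I error and the decision rule itself are not affected. This should be fixed, but it does not threaten the validity of the analysis.

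**What to change.** 1. Reconcile the safety confidence level between protocol 2.2.1 (95%) and 12.1.2 (97.5%), and state it in the SAP.
2. Replace the SAP's type II error and power statement. If the 95% limit applies to both endpoints, suitable wording is:

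> At an assumed true success rate of 96%, exact power per endpoint (one-sided 5%, Clopper-Pearson) is 81.0% with 20 subjects, 96.9% with 30 and 99.5% with 40. Study success requires rejection of both null hypotheses. If the two ratings are independent within a patient, the power for study success is 66%, 94% and 99%, respectively. Over all possible within-patient dependence it is 65% to 81% with 20 subjects.

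3. If the 97.5% safety limit is kept, give safety power as 81.0%, 88.3% and 97.9%, and joint power under independence as 66%, 86% and 97%.
4. In protocol 12.3, label the 81% explicitly as power for one endpoint.

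The cost is one SAP passage, one label in the protocol and one decision on the safety limit, with no extra subjects. The SAP allows revisions up to database lock. If lock has passed, the correction belongs in the final report, where protocol 12.6 places departures from the statistical plan. The only downside is a less favourable stated power.
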